6.2.3 Extracorporeal Volume

The American Association of Blood Banks' guidelines set a maximum extracorporeal blood volume to be $\leq 15\%$ of the patient's Total Blood Volume. A new calculation of Total Blood Volume is necessary before each treatment to estimate the safe extracorporeal blood volume that may be allowed for the patient undergoing treatment. These calculations should be performed

using the current weight and current hematocrit (the latter drawn after the last photopheresis treatment and within 48 hours before the next photopheresis treatment).

Maximum extracorporeal blood volume for patients weighing < 30 kg should not exceed 10% of the patient's Total Blood Volume. Patients who do not meet the safe minimal extracorporeal volumes listed in [Appendix D: Fluid Balance Management](#) should only be treated using a blood prime procedure. Patients who require but are not candidates for blood priming should not be enrolled and/or treated in the study. Please refer to [Appendix E: Blood Prime Technique Flow Sheet](#) for a worksheet to be used during the blood prime process and to [Appendix D: Fluid Balance Management](#) for detailed information on fluid management.

6.2.4 Anticoagulation During ECP

Anticoagulant Citrate Dextrose Formula-A (ACD-A) may be used instead of or in addition to heparin during ECP at the physician's discretion according to the patient's medical needs, provided that center-specific guidelines for the use of ACD-A with ECP and trained staff are available. Centers using ACD-A must have physician-approved protocols in place for managing hypocalcemia, a side effect of ACD-A administration. Protocols should include:

- Monitoring of ionized calcium levels.
- Determination of maximum RETURN flow rate parameters.
- Oral and/or intravenous calcium replacement.

General guidelines for monitoring and treating citrate toxicity are available in [Appendix F: ACD-A Recommendations for the Therakos CELLEX Photopheresis System](#); however, institutional guidelines and the judgment of medical staff must be used to dictate the appropriate intervention.

6.3 CORTICOSTEROIDS

6.3.1 Selection and Timing of Corticosteroid Doses in the Study

All patients enrolled in this trial will have received corticosteroids for the treatment of aGvHD. After entering the treatment period on study, it is suggested that the steroid dose be decreased by 12.5% to 25% of the dose after the initiation of ECP therapy if a sustained positive response to aGvHD has been observed for at least 3 consecutive days. The suggested goal is to have decreased the starting steroid dose by at least 50% at 4 weeks after initiation of ECP.

For patients taking a steroid other than methylprednisolone for the treatment of aGvHD, the daily dose should be converted to methylprednisolone equivalents at screening (to ensure the patient qualifies). Note, the steroid type and dose should be entered into the eCRF without this conversion.

6.4 ACUTE GVHD PROPHYLAXIS

Patients will be allowed to continue standard aGvHD prophylaxis regimens (e.g., cyclosporine, tacrolimus, methotrexate, and mycophenolate mofetil), without the addition of new therapies. Patients will be allowed to discontinue prophylaxis regimens for reasons of toxicity and will also be allowed to switch to another prophylaxis medication within the same class (e.g., the calcineurin inhibitors cyclosporine and tacrolimus) for reasons of toxicity.

6.5 CONCOMITANT MEDICATIONS

Any medication the patient takes, including herbal and other nontraditional remedies, during the 16-week study is considered a concomitant medication. All concomitant medications must be recorded in the eCRF. The following information must be recorded in the eCRF for each concomitant medication: generic name, route of administration, start date, stop date, dosage (average daily dose is acceptable), and indication. Any changes in the dosage or regimen of a concomitant medication must be recorded in the eCRF.

At Screening, medications that patients have taken during the last 30 days, including current medications, will be recorded. Prior administration of immunosuppressive agents to treat aGvHD other than steroids is not permitted. The prior use of non-absorbable corticosteroids is permitted. All concomitant medications taken by patients during the study to Week 16, including those medications taken between visits, will be recorded on the Prior and Concomitant Medication Report Form of the eCRF.

6.5.1 Prohibited Concomitant Medications

Prohibited concomitant medications include those used for the treatment of aGvHD (with the exception of steroids), medications that are not considered part of a standard prophylactic regimen, and systemic immunosuppressive or biologic therapies used for the treatment of other medical conditions.

6.6 EARLY CESSATION OF STUDY PARTICIPATION

If the Principal Investigator, the Sponsor, or the Medical Monitor becomes aware of conditions that suggest a risk to safe participation in the study, study treatment will be discontinued. If the Principal Investigator, based on his/her medical judgment, determines there is a risk to the patient with continued participation in the study, the patient will be withdrawn. The study may also be terminated early for all patients at the Sponsor's discretion. Conditions that may warrant termination include, but are not limited to:

- The discovery of an unexpected, significant, or unacceptable risk to the patients enrolled in the study.
- Failure to enroll patients at an acceptable rate.
- A decision on the part of the Sponsor to suspend or discontinue development of the drug.
- Recommendation by the Data Safety Monitoring Board (DSMB).

6.6.1 Early Cessation of Study Treatment

Patients *may* voluntarily stop receiving therapy at any time. The patient's legal guardian/legally authorized representative may choose to stop a patient's therapy at any time.

If a patient voluntarily ceases to receive therapy, the primary reason must be requested and, if provided, will be recorded on the Study Termination page of the eCRF.

The Principal Investigator and/or the Sponsor may also judge that early cessation of treatment is warranted for any one of the following reasons:

- Occurrence of AEs that pose a risk to safe participation.

- Abnormal laboratory value(s) that pose a risk to safe participation.
- Abnormal test procedure result(s) that pose a risk to safe participation.
- Unsatisfactory therapeutic effect.
- Condition no longer requires treatment.
- Significant protocol deviation.
- Patient non-compliance with protocol requirements.

Unless a patient/legal guardian/legally authorized representative withdraws study consent, patients will continue to be followed as per the trial protocol and clinical assessment schedule to ensure that full, intent-to-treat follow-up data are obtained.

For patients who are lost to follow-up, the Principal Investigator should show due diligence by documenting in the source documents steps taken to contact the patient (e.g., dates of telephone calls, emails).

Patients who voluntarily cease to receive treatment early will not be replaced. Patients will be replaced if they are enrolled in the trial but are not treated.

If a patient has received any ECP treatments and is administered a second-line therapy other than ECP for the treatment of aGvHD, or discontinues study treatment, that patient will be considered a nonresponder and may not be replaced.

7. STUDY CONDUCT

7.1 SCHEDULE OF ASSESSMENTS

Table 1. Schedule of Assessments

Assessments and Procedures	Screening	Treatment Period, weeks (+/- 2 days)												Follow-Up Period, weeks		Early Study Termination
		1	2	3	4 (Day 28) Primary Endpoint	5	6	7	8 (Day 56) Secondary Endpoint	9	10	11	12 (Day 84) Secondary Endpoint	16	26	
Informed consent/assent form	X															
Inclusion/exclusion criteria	X															
Focused medical history	X															
Transplant history	X															
Corticosteroid dosing	X	X	X	X	X	X	X	X	X	X	X	X	X	X		X
Complete physical examination	X				X				X				X	X		X
Targeted physical examination		X	X	X		X	X	X		X	X	X				
Urine Pregnancy test ^a	X	X	X	X	X	X	X	X	X	X	X	X	X			X
Vital signs	X	X	X	X	X	X	X	X	X	X	X	X	X	X		X
Lansky Performance Status	X				X				X				X	X		X
Local laboratory analyses ^b	X	X	X	X	X	X	X	X	X	X ^h	X	X	X	X		X
Assess aGvHD status ^c	X	X	X	X	X	X	X	X	X	X	X	X	X ⁱ	X		X
Baseline total bilirubin level and aGvHD assessment ^d		X														
Total bilirubin level and primary endpoint aGvHD status assessment ^e					X											
Total bilirubin level and secondary endpoint aGvHD status assessment ^f									X				X			
Number of ECP treatments ^g		3	3	3	3	2	2	2	2	2	2	2	2			

Concomitant medications	X	X	X	X	X	X	X	X	X	X	X	X	X	X	X	X
Adverse events	X	X	X	X	X	X	X	X	X	X	X	X	X	X	X	X
Nonrelapse mortality		X	X	X	X	X	X	X	X	X	X	X	X	X	X	X
Survival		X	X	X	X	X	X	X	X	X	X	X	X	X	X	X
Early study termination ^j																X

^a If the result of the urine test is positive, blood must be drawn for a serum human chorionic gonadotropin (HCG) level and analyzed locally. A serum test may be performed in place of the urine test.

^b At a minimum, a bilirubin level should be checked before the first ECP treatment of each week to assist in assessing aGvHD status of the previous week. Platelets and total WBC count should be checked before each scheduled ECP treatment as clinically indicated to ensure that they meet pre-ECP safety parameters. Hematocrit should be checked according to the CELLEX System Operator’s Manual. Ionized calcium may be checked, at the discretion of the Principal Investigator. A new calculation of Total Blood Volume is necessary before each treatment to estimate the safe extracorporeal blood volume that may be allowed for the patient undergoing treatment. These calculations should be performed using the current weight (recorded at the first visit of the week) and current hematocrit (drawn after the last photopheresis treatment and within 48 hours before the next photopheresis treatment).

^c After the baseline aGvHD assessment at the beginning of Week 1, aGvHD assessments should be performed within the weekly treatment window (± 2 days) after the last ECP treatment of each treatment week.

^d A baseline aGvHD assessment, including blood sampling for total bilirubin should be performed before the first ECP treatment of Week 1.

^e The assessment of aGvHD for the primary endpoint must occur at Day 28 (± 2 days) and must include a total bilirubin level.

^f The assessment of aGvHD for the secondary endpoint must occur at Days 56 and 84 (± 2 days) and must include a total bilirubin level.

^g Patients should be told emphatically to wear UVA-absorbing, wrap-around sunglasses and to cover exposed skin or use a sunblock (SPF 15 or higher) for the 24 hour period following treatment with methoxsalen, whether exposed to direct or indirect sunlight in the open or through a glass window.

^h These laboratory assessments should be performed monthly, before the first ECP treatment of the week at Weeks 5 and 9:

- CBC with differential (WBC, platelets, hemoglobin, hematocrit, neutrophils, lymphocytes, basophils, eosinophils, and monocytes); absolute neutrophil count.
- Electrolyte panel (sodium, potassium, chloride, bicarbonate, BUN, creatinine, and glucose), BUN/creatinine ratio, calcium, phosphorous, and magnesium.
- AST, ALT, GGT, total bilirubin, direct bilirubin, indirect bilirubin, alkaline phosphatase, and lactate dehydrogenase.

ⁱ The assessment of aGvHD must be +/- 2 days of the endpoint assessments

^j Early study termination applies to only to those patients who discontinue ECP prior to 12 weeks of treatment and do not remain on the study.

7.2 STUDY ASSESSMENTS AND PROCEDURES

7.2.1 Screening Period

The Screening Period begins once a patient signs the ICF, and will consist of at least one screening visit. If a patient does not meet the eligibility criteria, the patient will be considered a “screening failure” and will be discharged from the study. A small set of eCRF pages (i.e., a “Screening Failure Packet”) will be completed for those patients who are not eligible for this study.

Informed Consent/Assent

Patient consent/assent must be obtained before a patient’s participation in ANY study-related procedures. A copy of the signed and dated ICF will be given to the patient, legal guardian or legally authorized representative. The original signed and dated ICF will be maintained at the study site. The date(s) of signed consent must be recorded in the eCRF. For more information, see [Section 10.7 Informed Consent/Assent](#).

Inclusion/Exclusion Criteria

The inclusion and exclusion criteria MUST be assessed for patient eligibility at screening and recorded on the Inclusion Criteria and Exclusion Criteria Forms of the eCRF. Patients who do not meet the inclusion and exclusion criteria will be considered “screening failures” and will be discharged from the study.

Focused Medical History

The medical history should include any medical condition that the patient recalls or that is part of the medical record that is relevant to the condition under study. Any condition present at the onset of the study should be noted. Any condition NOT listed on the Medical History and Review of Symptoms Form of the eCRF will be considered an AE if it occurs during the course of the study (i.e., any time after the patient has signed the ICF). Any condition that increases in frequency or worsens as compared to the Medical History and Review of Symptoms Form of the eCRF will also be considered an AE.

Transplant History

Background information about a patient’s transplant (e.g., date of transplant, type of bone marrow transplant, underlying condition [malignant or non-malignant]) will be recorded on the Transplant History Form of the eCRF.

Corticosteroid Dosing History

The patient’s steroid dosing for the treatment of aGvHD for the 30 days prior to screening must be documented on the Corticosteroid Dosage Form of the eCRF. Dosages will be recorded as given in the eCRF, but the methylprednisolone equivalent dosage must be assessed to ensure compliance to the 2.0 mg/kg dosage required for inclusion into the study.

Physical Examination

A qualified health-care professional will give each patient a complete physical examination in order to capture general health by organ system. Patient height and weight will also be recorded.

Pregnancy Test

At the screening visit, a urine dipstick pregnancy test will be performed through local laboratory for all females of childbearing potential, defined as those who have reached the onset of menarche or 8 years of age, whichever comes first. A serum test may also be performed in place of a urine dipstick. If the urine dipstick result is positive, blood must be drawn for a serum human chorionic gonadotropin (HCG) level and analyzed locally. A positive serum HCG result will prohibit the patient from enrollment into the study.

Vital Signs

Diastolic and systolic blood pressure, pulse rate, respiratory rate, and temperature will be taken at the screening visit.

Lansky Performance Status

A qualified health-care professional (physician, physician's assistant, nurse practitioner) will evaluate the patient's Health Performance Status using the Lansky Performance Status Scale ([Appendix C: Lansky Scale](#)).

Local Laboratory Analyses

Laboratory assessments (including pregnancy tests) will be performed through a local laboratory. The data obtained should be entered into the eCRF.

Clinically significant laboratory abnormalities should be recorded as AEs according to the Principal Investigator's judgment. Blood samples may be obtained through standard venipuncture technique or through a venous access catheter, according to institutional guidelines.

At the screening visit, a blood sample will be collected for the purpose of assessing eligibility and processed for:

- CBC with differential (WBC, platelets, hemoglobin, hematocrit, neutrophils, lymphocytes, basophils, eosinophils, and monocytes) and an absolute neutrophil count.
- Electrolyte panel (sodium, potassium, chloride, bicarbonate, BUN, creatinine, and glucose), blood urea nitrogen (BUN)/creatinine ratio, calcium, phosphorus, and magnesium.
- AST, ALT, gamma-glutamyltransferase (GGT), total bilirubin, direct bilirubin, indirect bilirubin, alkaline phosphatase, and lactate dehydrogenase.
- Coagulation panel (PT/PTT, INR).

If any of these samples were drawn within the preceding 72 hours and the results are available, they do not have to be re-drawn and may be used to assess eligibility.

A total bilirubin level will also be assessed before the first ECP treatment of the study at Week 1, and this value will be used for the baseline assessment of a patient's aGvHD status.

Please refer to [Section 4.1](#) and [Section 4.2](#) for the values of specific local laboratory results that would exclude patients from this study.

Assessment of aGvHD Status

Patients will be evaluated to confirm that they have steroid-refractory aGvHD grade B-D. Steroid-refractory is defined as progressive aGvHD after 3 days of or no response after 5 days of starting systemic steroids at a dose of 1.0 mg/kg/day methylprednisolone or equivalent. Patients with grade A are not eligible for this study. Grade D organ involvement will be limited to skin and liver.

Patients will be evaluated by the treating physician for the presence or absence of aGvHD manifestations of the skin, liver, and gut. Source data will be collected for each patient and entered into the eCRF, and a scoring algorithm will later be applied to calculate the grade of aGvHD using the modified IBMTR Severity Index and the modified Glucksberg criteria.

Skin aGvHD Staging

Only active rash (erythema) is considered in body surface area (BSA) calculations. Hyper- (e.g., brown/tanned rash) or hypopigmentation representing post-inflammatory changes are not included in the BSA assessment. Skin involvement will be reported as % BSA using the Rule of Nines ([Appendix G: Percent Body Surface Area Assessment](#)) [Waslen, 1986] and/or presence of bullae.

Other common etiologies for skin symptoms include drug rash, conditioning regimen toxicity, infection, and cytokine storm/engraftment syndrome.

Liver aGvHD Staging

Bilirubin will be assessed on the day of the first ECP treatment, and this value will be used for the baseline assessment of a patient's aGvHD status. Total bilirubin (not direct/conjugated bilirubin) will be used for staging.

Other common etiologies for liver symptoms include drug toxicity, conditioning regimen toxicity, veno-occlusive disease, total parenteral nutrition, cholestasis, and infection.

Gut aGvHD Staging

Stool output will be reported as volumes for all inpatients and as episodes (frequency and consistency) for all outpatients. Patients weighing ≥ 50 kg will be graded using total stool volume per day (mL/day), while patients weighing < 50 kg will be evaluated for gut symptoms according to mL/kg/day, as a function of body weight.

For patients who weigh < 50 kg, every effort should be made to collect stool volumes as a daily average in milliliters over a 3-day period. For diarrhea volumes, report liquid stool volume in the following order:

1. Average of 3 consecutive days, if available.
2. Otherwise, the 3 days closest to each other within 1 week.
3. Otherwise, the average of 2 consecutive days.
4. Otherwise, the maximum volume from the isolated day(s) available.

Formed or mostly formed stools should not be quantified or counted in the estimation of liquid stool volume. It will be noted on the source document, if urinary mixing is present.

For inpatients in diapers, the volume will be calculated from the weight of the diaper before and after use. For outpatients, Patient Stool Volume records will be provided, according to usual site practice, along with instructions for collection and measurements. Stool volume collection should be done without regard to the ECP treatment schedule.

When diarrhea is reported as episodes instead of individual volumes, episodes of non-quantified liquid stool will be counted as 200 mL each for patients ≥ 50 kg and 4 mL/kg for patients < 50 kg.

When gross blood is present:

- Bloody diarrhea is staged as 4, even if low volume.
- Blood-streaked low volume (< 500 mL/day or < 10 mL/kg/day) stools (as can be seen with bleeding hemorrhoids, for example) are staged as 0.

For stage D or stage 4 gut involvement, severe pain is defined as:

- Pain that requires the start of narcotic use, or an increase in on-going narcotic use PLUS.
- Pain that significantly impacts performance status, as determined by the treating physician.

Other common etiologies for GI symptoms include drug toxicity, conditioning regimen toxicity, and infection.

Upper GI aGvHD Staging

For patients with isolated upper GI symptoms, pre-Screening biopsy results will be used to confirm the diagnosis of aGvHD. The determination that nausea, vomiting and/or anorexia are persistent is based on clinical judgment. As a general rule, nausea lasting fewer than 3 days, fewer than 2 vomiting episodes per day for at least 2 days, and anorexia without weight loss should not be considered persistent.

Other common etiologies for upper GI symptoms include drug toxicity, conditioning regimen toxicity, infection, and total parenteral nutrition.

Concomitant Medications

Medications that patients have taken during the last 30 days, including current medications, will be recorded. Medications for the treatment of aGvHD will be captured individually on a separate eCRF page(s). Other medications that patients are taking at screening will be captured on the Concomitant Medication Form ([Section 6.5](#)). Concomitant medications for screening failures will not be recorded on the eCRF.

Adverse Events

Patients will be asked about AEs that may have occurred after the patient signed and dated the ICF. Each patient will be asked about AEs using the non-specific question, "How have you been since your last visit?" Any AEs elicited by this question will be recorded on the Adverse Event Report Form of the eCRF, as well as any AEs spontaneously volunteered by the patient or observed by the study staff.

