Study assessments	
Grading and Assessment of aGvHD:
 
 • Acute GvHD will be assessed for each organ system by the treating physician, and source data will be collected for each patient and entered into the eCRF. A scoring algorithm will then be applied to calculate the grade of aGvHD using the modified IBMTR Severity Index and the modified Glucksberg criteria. Acute GvHD status will be assessed at screening and once per week throughout the Treatment and at each Follow-up Period by the treating physician. • The formal statistical analysis and evaluation of response is based on at least 4-weeks of ECP treatment only. 
Cumulative Steroid Dose:
 
Cumulative daily steroid dose from diagnosis of aGvHD along with all other concomitant medications will be recorded every week during the Treatment Period (Week 12).
 
Adverse Events:
 
Adverse events will only be recorded from ICF signing until Week 16. Following Week 16, there will be a passive chart review which will not include the collection of AEs.
 
Treatment Failure:
 
Treatment failure is defined as the addition of next-line systemic therapy for the treatment of aGvHD. Next-line treatment is defined as any additional systemic treatment not used for initial treatment of aGvHD, or for prophylaxis. Next-line treatment also includes an increase in steroid dose to $>$ 2.0 mg/kg/day of methylprednisolone equivalents because of a flare during steroid tapering. A flare is defined as any increase in aGvHD symptoms after an initial response (CR or PR).

Power and sample size	
A total of 48 patients with steroid-refractory grade B-D aGvHD will be enrolled and receive at least one ECP treatment. The trial is designed to test the null hypothesis that standard therapy has an overall response (CR+PR)

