2.2 SECONDARY OBJECTIVES

- To assess the safety of ECP.
- To assess the duration of response to ECP.
- To assess the steroid-sparing effect of ECP.
- To assess the organ-specific response to ECP.

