3.1 OVERVIEW

Screening will occur in a single visit during which patients will be evaluated for eligibility and for the grading of aGvHD. Patients with steroid-refractory aGvHD grade B-D who meet the eligibility criteria will be treated with UVADEX (methoxsalen) Sterile Solution in conjunction with the CELLEX System. Patients must be enrolled and receive their first ECP treatment within 1 week (7 days) after being diagnosed as having steroid-refractory aGvHD. Patients are expected to receive the stated number of ECP treatments per treatment week (7 days) \pm 2 days, and a total of no more than 12 ECP treatments for the first 28 days. A maximum of 28 ECP treatments will be given per patient during the 12-week treatment period. Conventional steroids will continue to be administered and tapered based on a sustained response to ECP. The primary endpoint is the proportion of patients reaching an overall response (CR+PR) after 4 weeks (Day 28) of ECP treatment, or fewer treatments if they discontinued treatment, regardless of steroid tapering.

The addition of next-line systemic therapy for aGvHD will be considered a treatment failure. Next-line treatment is defined as any additional systemic treatment not used for initial treatment of aGvHD, or for prophylaxis. Next-line treatment also includes an increase in steroid dose to > 2.0 mg/kg/day of methylprednisolone equivalents because of a flare during steroid tapering. A flare is defined as any increase in aGvHD symptoms after an initial response (CR or PR). Patients will be allowed to continue standard aGvHD prophylaxis regimens (e.g., cyclosporine, tacrolimus, methotrexate, and mycophenolate mofetil) without the addition of new therapies. Patients will be allowed to discontinue prophylaxis regimens for reasons of toxicity, and will also be allowed to switch to another prophylaxis medication within the same class (e.g., the calcineurin inhibitors cyclosporine and tacrolimus) for reasons of toxicity.

After completion of the 12-week Treatment Period, patients may continue ECP treatment on commercial product at the discretion of the Principal Investigator. Acute GvHD status will be assessed 4 weeks after completion of the Treatment Period, and survival will be assessed by passive follow-up (chart review) 26 weeks after initiation of ECP treatment.

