3.2.2 Secondary Endpoints

- Safety parameters including vital signs, laboratory tests, and spontaneously reported AEs and SAEs.

- Proportion of patients who achieve an overall response 8 weeks (Day 56) and 12 weeks (Day 84) after initiation of ECP treatment.
- Duration of response (defined as the length of time a patient maintains a response through Week 16 of the Follow-up Period on a per-patient basis).
- Proportion of patients who achieve an overall response after 4 weeks (Day 28), 8 weeks (Day 56), and 12 weeks (Day 84) of ECP treatment according to the modified Glucksberg criteria ([Appendix B: Modified Glucksberg Criteria](#)).
 - Source data will be collected for each patient and entered into the eCRF, and a scoring algorithm will be applied to calculate the grade of aGvHD using the modified Glucksberg Criteria.
- Cumulative dose of daily steroids administered from diagnosis of aGvHD to 12 weeks (Day 84) after initiation of ECP treatment.
- Organ-specific grade at 4 weeks (Day 28), 8 weeks (Day 56), and 12 weeks (Day 84) after initiation of ECP treatment.

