7.2.2 Treatment Period

The following assessments and procedures should be performed during the Treatment Period. Not all of the assessments and procedures listed below are to be performed at every scheduled visit (e.g., selected assessments are performed at Weeks 4 and 8). For the timing of when to administer individual assessments and procedures, see the Schedule of Assessments in [Table 1, Section 7.1](#). Unless otherwise indicated, assessments should be performed before the first ECP treatment of the week.

Corticosteroid Dose Record

The patient's steroid dosing for the treatment of aGvHD must be documented on the Corticosteroid Dosage Form of the eCRF. Dosages should be recorded without modification (although average daily dose is acceptable). Methylprednisolone equivalence will be calculated later.

Physical Examination

A qualified health-care professional will give each patient a complete physical examination to document any changes in the general health of the patient by organ system. The complete physical examinations will be performed after all other assessments included in Weeks 4, 8, 12 and 16 have been completed. Targeted physical examinations will be performed after all other assessments included in Weeks 1, 2, 3, 5, 6, 7, 9, 10, and 11 have been completed. Patient height and weight will also be recorded each week. In those weeks when patients are reporting to the study site multiple times, height and body weight need only be recorded at the first visit.

A new calculation of Total Blood Volume is necessary before each treatment to estimate the safe extracorporeal blood volume that may be allowed for the patient undergoing treatment. These calculations should be performed using the current weight (recorded at the first visit of the week) and current hematocrit (drawn after the last photopheresis treatment and within 48 hours before the next photopheresis treatment).

Pregnancy Test

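### The steroid-sparing endpoint pools dose given before ECP with dose on ECP, and the protocol is inconsistent about how far back steroid dosing is collected

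*Combined protocol and SAP*

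**What the plan says.** One secondary objective (Section 2.2) is "To assess the steroid-sparing effect of ECP". The endpoint that serves it (Section 3.2.2, repeated in the Synopsis and Section 9.3.2) is "Cumulative dose of daily steroids administered from diagnosis of aGvHD to 12 weeks (Day 84) after initiation of ECP treatment". It makes no split at the first ECP treatment.

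Three places describe how steroid dosing is collected:

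- Synopsis, Study assessments: "Cumulative daily steroid dose from diagnosis of aGvHD along with all other concomitant medications will be recorded every week during the Treatment Period".
- Section 7.2.1, Corticosteroid Dosing History: at screening the patient's "steroid dosing for the treatment of aGvHD for the 30 days prior to screening must be documented on the Corticosteroid Dosage Form". The next sentence ties this history to the 2.0 mg/kg entry limit.
- Section 7.2.2, Corticosteroid Dose Record: during treatment the patient's "steroid dosing for the treatment of aGvHD must be documented on the Corticosteroid Dosage Form of the eCRF". Table 1 schedules this at every week from Week 1 to Week 12.

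The general medication history has the same look-back as 7.2.1: "At Screening, medications that patients have taken during the last 30 days, including current medications, will be recorded" (Section 6.5, and again in 7.2.1). The fields kept for each medication are "generic name, route of administration, start date, stop date, dosage (average daily dose is acceptable), and indication".

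On timing, Section 3.1 says "Patients must be enrolled and receive their first ECP treatment within 1 week (7 days) after being diagnosed as having steroid-refractory aGvHD". That clock starts at the steroid-refractory diagnosis. No criterion in Sections 4.1 or 4.2 limits the time from aGvHD diagnosis to screening.

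For analysis, Section 9.3.2 plans a repeated-measures mixed model of daily steroid dose. It names no method for the cumulative dose.

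**The concern.** There are two separate problems.

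The first is what the endpoint measures. Every patient has received steroids for aGvHD before ECP (Section 6.3.1), and that dose cannot be spared by ECP. A total that starts at diagnosis therefore varies with how long the patient was treated before entry, as well as with what happened on ECP. With no control arm, nothing balances that variation.

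The second is whether the total can be computed as defined. The endpoint opens at diagnosis, but the only operational instructions for pre-study dosing reach back 30 days. For a patient diagnosed earlier than that, a site following 7.2.1 to the letter would leave the first part of the sum empty. The undercount would fall on the patients with the longest steroid exposure and would make their totals look smaller than they were.

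**Working it through.** The protocol gives no expected value, power or sample size for this endpoint, so there is no figure to reproduce. The check is a comparison of windows, a day count and an illustrative dose sum.

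**Windows.** The endpoint runs from aGvHD diagnosis to Day 84. Required collection runs from 30 days before screening, then weekly through Week 12. The two agree only if diagnosis falls within 30 days of screening, or if sites act on the synopsis sentence. That sentence describes weekly recording during treatment; it does not say how doses older than 30 days are to be retrieved. A medication start date shows when a drug began but does not give the dose history in between.

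**Day count.** Section 4.1 gives three timed routes to refractory status: progression at 3 days, no improvement by 5 days, and no complete response after 2 weeks. Assume that steroids start at aGvHD diagnosis, that refractory status is declared as soon as it is met, and that the full 7 days to first ECP are used:

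- 3 + 7 = 10 days
- 5 + 7 = 12 days
- 14 + 7 = 21 days

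All three are under 30 days, so nothing is lost on these timelines. The 2-week route has no upper limit, however, so later entry is allowed.

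**Dose sum (assumed pattern).** Let the dose be constant at D for L days before first ECP, with screening on the day of first ECP. On treatment, let it fall linearly to 50% of D at Day 28, matching the suggested goal in Section 6.3.1, and then linearly to a fraction f of D at Day 84, with f from 0 to 0.5. This pattern is for illustration only.

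On-treatment total, in units of D:

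- Days 1–28: 28 × 0.75 = 21
- Days 29–84: 56 × 0.5 + (f − 0.5) × 28.5, which is 13.75 at f = 0 and 28 at f = 0.5
- Sum S: 34.75 at f = 0 and 49 at f = 0.5

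Pre-ECP share = L / (L + S). Share missed by a 30-day look-back = (L − 30) / (L + S) for L above 30, otherwise 0. D cancels from both.

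| L (days) | Pre-ECP share | Missed |
|---|---|---|
| 10 | 17–22% | 0% |
| 21 | 30–38% | 0% |
| 30 | 38–46% | 0% |
| 45 | 48–56% | 16–19% |
| 60 | 55–63% | 28–32% |
| 90 | 65–72% | 43–48% |

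For example, at L = 45 and f = 0 the missed share is 15 / 79.75 = 19%; at f = 0.5 it is 15 / 94 = 16%.

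**Effect of pooling on comparisons between patients.** Take two patients with the same on-treatment course (f = 0.25, S = 41.875), one with 10 and one with 21 days of prior steroids. Their totals are 51.875 and 62.875, a ratio of 1.21. The second looks 21% worse on the endpoint although the two did equally well on ECP.

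**The case against.** A reader might infer that sites collect only 30 days and that the endpoint is therefore truncated. The documents do not support that. The synopsis is part of the same protocol and says dose from diagnosis is recorded. Section 7.2.1 sets a minimum and does not bar older doses. Its 30-day window has a visible eligibility purpose, since exclusion criterion 3 also uses 30 days, counted to first study treatment. Section 7.2.1 sends aGvHD medications to separate eCRF pages whose content is not in the text. What remains is a contradiction to reconcile, and truncation only if sites stop at what 7.2.1 requires.

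A reader might also infer a large loss in typical patients. A steady 2 mg/kg/day for 45 days before screening, then a mean of 1 mg/kg/day for 84 days, gives 90 + 84 = 174 mg/kg. Of this, 60 + 84 = 144 is captured, so 17% is missing. But a patient on that course who was not in complete response would have met the 2-week criterion about a month before screening. This is an unusual case, and on the 10–21 day timelines the loss is zero.

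On pooling, the fair reply is that pre-ECP dose is the only within-patient reference in a single-arm trial, so it would be too strong to say that it tells us nothing about sparing. The planned model of daily dose could separate the two periods, and Section 9.3 leaves details to a formal analysis plan that is not in the text available here. Both points stand. They soften the concern for the modelled analysis. They do not change the cumulative endpoint, which as defined adds the two periods together.

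**Conclusion.** The point holds in two parts.

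- **Pooling.** This follows from the definition and touches every patient. Under the assumed constant pre-ECP dose and suggested taper, the pre-ECP share is about 17–38% after 10–21 days of prior steroids and rises with longer disease.
- **Collection window.** The synopsis and Section 3.2.2 start at diagnosis, while Sections 7.2.1 and 6.5 require 30 days. If sites follow 7.2.1, the total is left-truncated for patients diagnosed more than 30 days before screening. The loss is 0% up to 30 days, about 16–19% at 45 days and 28–32% at 60 days under the same assumptions. The documents do not say how many such patients there will be.

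This is a secondary endpoint with no stated hypothesis, and the primary test does not depend on it. It is still worth correcting, because it is the endpoint attached to a named objective and the remedy is cheap.

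**What to change.** 1. In the Synopsis and Sections 3.2.2 and 9.3.2, make the steroid-sparing measure the cumulative methylprednisolone-equivalent dose in mg/kg from Day 1 to Day 84. Report pre-ECP dose separately, with its window stated. Steroid dose and weight are already recorded weekly from Week 1 to Week 12, and conversion to methylprednisolone equivalents is already planned, so no new data are needed.
2. If the from-diagnosis total is kept as a descriptive measure, reconcile Section 7.2.1 with the Synopsis and Section 3.2.2 by having sites record steroid dosing back to the date of aGvHD diagnosis.

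The first change costs only wording and programming. The second costs a longer chart abstraction for patients diagnosed more than 30 days before screening, probably a few. Neither alters treatment, eligibility or the primary analysis.
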